6.1 Table, Listing, and Figure Format

6.1.1 General

1. All TLFs will be produced in landscape format.
2. All TLFs will be produced using the Times New Roman font, size 8 (minimum).

3. The data displays for all TLFs will have a 1.5-inch binding margin on top of a landscape oriented page and a minimum 1-inch margin on the other 3 sides.
4. Headers and footers for figures will be in Times New Roman font, size 8 (minimum).
5. Legends will be used for all figures with more than 1 variable, group, or item displayed.
6. TLFs will be in black and white (no color).
7. Only standard keyboard characters will be used in the TLFs. Special characters, such as non-printable control characters, printer-specific, or font-specific characters, will not be used. Hexadecimal-derived characters will be used, where possible, if they are appropriate to help display math symbols (e.g., μ). Certain superscripts (e.g., cm^2) will be employed on a case-by-case basis.
8. Mixed case will be used for all titles, footnotes, column headers, and programmer-supplied formats.

6.1.2 Headers

All output will have the following header at the top of the page:

Retrophin, Inc.
FOSMETPANTOTENATE (Phosphopantothenate
Replacement Therapy)
Clinical Study Number 024PKAN15004

Page n of N

All output will have page numbers. TLFs should be internally paginated in relation to the total length (i.e., the page number should appear sequentially as page n of N, where N is the total number of pages in the table).

6.1.3 Display Titles

Each TLF will be identified by a numeral, and the designation (i.e., Table 1) should be centered above the title. A decimal system (14.x-y-z, 14.x-y-z, and 16.2.x-y) will be used to identify TLFs with related contents. The title will be centered in initial capital characters. The analysis set will be identified on the line immediately following the title. The title and table designation will be single spaced. A solid line spanning the margins will separate the titles from the column headers. There will be 1 blank line between the last title line and the solid line.

Table 14.x-y-z
First Line of Title
Second Line of Title if Needed

Full Analysis Set

6.1.4 Column Headers

1. Column headings will be displayed immediately below the solid line described above, in initial upper-case characters.
2. For numeric variables, units will be included in column or row heading when appropriate.
3. Analysis set sizes will be presented for each treatment group in the column heading as (N=xx) (or in the row headings if applicable). This is distinct from the 'n' used for the descriptive statistics representing the number of patients in the analysis set.
4. The order of treatment labels in tables and listings will be: placebo, fosmetpantotenate for the double-blind treatment period; and Open-Label fosmetpantotenate (after Double-Blind placebo), Open-Label fosmetpantotenate (after Double-Blind fosmetpantotenate) for the open-label extension phase; and Total (if applicable for either phase of the study).

6.1.5 Body of the Data Display

1. Listings will be sorted for presentation in order of study phase, treatment group, as above, patient ID, collection day, and collection time.
2. For ordered categorical parameters, frequency tables will present all categories of the parameter between the minimum and maximum level, even if n=0 for all treatment groups in a given category. For example, the frequency distribution for symptom severity would appear as:

Severity Rating	n
severe	0
moderate	8
mild	3

Where percentages are presented in these tables, any counts of 0 will be presented as 0 and not as 0 (0%).

3. If the categories for a table are not ordered (e.g., Medical History, Reasons for Discontinuation from the Study, etc.), then only those categories for which there is at least 1 patient represented in 1 or more groups will be included.
4. An Unknown or Missing category will be added to the summary table of any categorical parameter for which information is not available for 1 or more patients.
5. Unless otherwise specified, the estimated mean and median for a set of values will be displayed to 1 more significant digit greater than the original values; standard deviation (SD) will be presented to 2 more significant digits than the original values. The minimum and maximum will be reported at the same number of significant digits as the original values. LSmeans will be reported to 1 decimal place, and corresponding CI's to 2 decimal places. For example, for systolic blood pressure:

n	XX
Mean	XXX.X
SD	X.XX
Median	XXX.X
Minimum	XXX
Maximum	XXX

6. Data in columns of a table will be formatted as follows:
 - alphanumeric values left-justified;
 - whole numbers (e.g., counts) right-justified; and
 - numbers containing fractional portions decimal-aligned.
7. Percentage values will be formatted with 1 digit to the right of the decimal point in parentheses, 1 space after the count (e.g., 7 (12.8%), 13 (5.4%)). Less-than signs (e.g., “<0.1%”) will appear when values are >0.0% and <0.1% (but not equal to 0.0%). Unless otherwise noted, the denominator for calculating percentages will be the number of patients in a given treatment group and analysis set.
8. Tabular displays of data for prior/concomitant medications and all tabular displays of adverse event data will be presented by body system, drug class, or SOC with the highest occurrence in the fosmetpantotenate treatment group for the double-blind period, or in the group maintained on fosmetpantotenate in the open-label extension phase, in decreasing order. Within the body system, drug class and SOC, medical history (by PT), drugs (by ATC2 code), and adverse events (by PT) will be displayed in decreasing order. If the incidences of multiple terms are identical, they will be sorted alphabetically.
9. Missing data will be left as blank in patient listings.
10. Dates will be formatted in SAS Date9 date format ddmmmyyy (e.g., “27Jan2018”). Missing portions of dates will be represented on patient listings as blank (e.g., “Jan2018”). Dates that are missing because they are not applicable for the particular patient will be presented as “N/A”, unless otherwise specified.
11. All observed time values will be presented using a 24-hour clock in hh:mm:ss format (e.g., “01:35:45”, “21:26”). Time values will be reported only if they were measured as part of the study.

6.1.6 Footnotes

1. A solid line spanning the margins will separate the body of the data display from the footnotes.
2. All footnotes will be left justified with single-line spacing immediately below the solid line underneath the data display.
3. Each new footnote will start on a new line.
4. Footnotes will appear on each page. Patient specific footnotes will generally be avoided.
5. Footnotes will be used sparingly, and only if they add value to the table, figure, or data listing. If a data display has more than 4 footnotes, they will all appear on a

cover page for the data display; only those footnotes essential for clarification of the data will be repeated on each page.

6. All abbreviations used in a given display will be defined in the corresponding footnote.
7. The last line of the footnote section will be a standard source line, indicating the data source used by the SAS program that produced the data display, the name of the SAS program, and the listing source (e.g., “Data source: xyzabc.sas7bdat Program source: myprogram.sas Listing source: 16.x.y.z”).

6.2 Data-Handling Rules

This section describes naming conventions and rules for calculations common to all applicable tables. Some rules specific to a table can be found in the relevant mock-ups.

6.2.1 Unit Conversion to Months/Years

If months are calculated for a duration, then the following conversion is used:

$$\text{Duration_in_months} = \text{Duration_in_days} / 30.42$$

If years are calculated for a duration, then the following conversion is used:

$$\text{Duration_in_years} = \text{Duration_in_days} / 365.25$$

6.2.2 Visits

Relative Study Day: The date of first dose of study treatment is Day 1. A minus (–) sign indicates days prior to date of first dose (e.g., Day -5 represents 5 days before first dose.) There is no Day 0.

If a visit is before the date of first dose, the relative study day is calculated as (Visit Date – Date of First Dose). Otherwise, the relative study day for a specific visit is calculated as (Visit Date – Date of First Dose +1).

- Baseline: For all study variables, baseline for the double-blind period is defined as the last measurement obtained prior to the first dose of double-blind study medication, unless otherwise specified; for the open-label extension study, baseline is the last measurement obtained prior to the first dose of open-label study medication (fosmetpantotenate).
- Post baseline: post baseline visits will be nominal visits, as scheduled in the protocol.

6.2.3 Demographics and Baseline Characteristics

- Height (in cm) = height (in inches) * 2.54
- Weight (in kg) = weight (in lbs) * 0.4535
- Body Mass Index (BMI) (kg/m^2) = weight (in kg) / [height (in meters)] **2

- Body Surface Area⁸ (BSA) (m²) = [height (cm) * weight (kg)/3600]^{1/2}

6.2.4 Prior and Concomitant Medications

Prior and concomitant medications will be coded and classified using the World Health Organization (WHO) Drug Dictionary Sep 2018 B3 Format.

When partial dates are present in the data, both a partial start date and/or a partial stop date will be evaluated to determine whether it can be conclusively established that the medication either ended prior to first dose of blinded investigational product or started after. If the above cannot be conclusively established based on the partial and/or present dates, then the medication will be counted as concomitant for the double-blind period and open-label period (if the patient has reached the open-label period).

The imputation method for the handling of missing or partial dates will be as follows. When the start date and the stop date are both incomplete for a patient, the start date will be imputed first:

Partial start date

Missing Month and Day

- If the year of the partial start date is the same as the year of the first dose of blinded investigational product, then the month and day of the first dose of blinded investigational product will be assigned to the missing fields.
- If the year of the partial start date is before the year of the first dose of blinded investigational product, *December 31* will be assigned to the missing fields.
- If the year of the partial start date is after the year of the first dose of blinded investigational product, *January 1* will be assigned to the missing fields.

Missing Month Only

- If only the month is missing, then the month only will be imputed according to the procedure above.

Missing Day Only

- If the month and year of the partial start date are the same as the month and year of the first dose of blinded investigational product, then the day of the first dose of blinded investigational product will be assigned to the missing day.
- If either the year of the partial start date is before the year of the date of the first dose of blinded investigational product or if both years are the same but the month of the partial start date is before the month of the date of the first dose of blinded investigational product, then the last day of the month will be assigned to the missing day.
- If either the year of the partial start date is after the year of the date of the first dose of blinded investigational product or if both years are the same but the month of the incomplete start date is after the month of the date of the first dose of

blinded investigational product, then the first day of the month will be assigned to the missing day.

If the stop date is complete and the imputed start date as above is after the stop date, then the start date will be imputed with the stop date.

Partial stop date

Missing Month and Day

- If the year of the partial stop date is the same as the year of the last dose of investigational product (double-blind or open-label), then the month and day of the last dose of investigational product (double-blind or open-label) will be assigned to the missing fields.
- If the year of the incomplete stop date is before the year of the last dose of investigational product (double-blind or open-label), *December 31* will be assigned to the missing fields.
- If the year of the incomplete stop date is after the year of the last dose of investigational product (double-blind or open-label), *January 1* will be assigned to the missing fields.

Missing Month Only

- If only the month is missing, then the month only will be imputed according to the above procedure.

Missing Day Only

- If the month and year of the partial stop date are the same as the month and year of the last dose of investigational product (double-blind or open-label), then the day of the last dose of investigational product (double-blind or open-label) will be assigned to the missing day.
- If either the year of the incomplete stop date is before the year of the date of the last dose of investigational product (double-blind or open-label) or if both years are the same but the month of the partial stop date is before the month of the date of the last dose of investigational product (double-blind or open-label), then the last day of the month will be assigned to the missing day.
- If either the year of the partial stop date is after the year of the date of the last dose of investigational product (double-blind or open-label) or if both years are the same but the month of the partial stop date is after the month of the date of the last dose of investigational product (double-blind or open-label), then the first day of the month will be assigned to the missing day.

If the imputed stop date is before the start date (imputed or non-imputed start date), then the imputed stop date will be equal to the start date.

6.2.5 Adverse Events

Adverse events will be coded and classified using the MedDRA coding dictionary Version 20.0. The specific dictionary version will appear in the actual tables/listings.

AEs with missing start and end dates will be considered as treatment emergent for the open-label period, taking a “worst-case” approach. If the patient has not yet reached the open-label period, or if the AE has a stop date overlapping with the double-blind study period, then the AE will be counted as treatment-emergent for the double-blind period.

PAREXEL International Electronic Signature Page

This page is the manifestation of the electronic signature(s) used in compliance with PAREXEL International's electronic signature policies and procedures and in compliance with applicable regulations.

UserName: PPD

Title: PPD

Date: Monday, 22 April 2019, 05:21 PM GMT Standard Time

Meaning: Document contents authored.

UserName: PPD

Title: PPD

Date: Wednesday, 24 April 2019, 01:41 AM GMT Standard Time

Meaning: Document contents reviewed.

UserName: PPD

Title: PPD

Date: Monday, 29 April 2019, 11:18 AM GMT Standard Time

Meaning: Document contents reviewed.

UserName: PPD

Title: PPD

Date: Monday, 29 April 2019, 01:22 PM GMT Standard Time

Meaning: Document contents reviewed.

UserName: PPD

Title: PPD

Date: Monday, 29 April 2019, 02:09 PM GMT Standard Time

Meaning: Document contents approved.

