6.5.2.2. Open-Label Period

Patients will receive open-label fosmetpantotenate after they complete the double-blind period of the study. No dose escalation is required for the open-label period. All patients (regardless of randomization assignment for the double-blind period) will initiate treatment with fosmetpantotenate in the open-label period according to the dose of study medication they were receiving at the end of the double-blind period; for patients 6 to <18 years of age, the initial dose may be adjusted, if needed, based on the patient's weight at the end of the double-blind period.

For patients 6 to <18 years of age, the dose will be adjusted as needed during the open-label period based on their weight taken at study visits every 24 weeks.

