4.11 Safety Analysis

For the Interim Analysis, the safety analyses will cover all data collected until the database cut-off, including data from the open-label period. Safety analyses will be performed using data from the Double-Blind and Open-Label Safety Populations. Tables using the Double-Blind Safety Population will include only data collected during the

double-blind period. Tables using the Open-Label Safety Population will include only data collected during the open-label period.

In addition, select safety analyses will be performed using the Fosmetpantotenate Safety Population. Tables using the Fosmetpantotenate Safety Population will include data collected following the first exposure for fosmetpantotenate (i.e., double-blind and open-label data for patients administered fosmetpantotenate at baseline of double-blind period, open-label data only for patients first administered fosmetpantotenate at baseline of the open-label period.)

Safety of fosmetpantotenate will be determined on the basis of treatment-emergent AEs (TEAEs), vital signs, weight, physical examinations, clinical laboratory assessments, the Columbia Suicide Severity Rating Scale (C-SSRS) (in assessable patients), and ECG findings.

For the Double-Blind Safety Population, table summaries and figures will be presented by treatment group as appropriate; for the Open-Label and Fosmetpantotenate Safety Populations, safety summaries will be presented for the entire cohort, and (when indicated) by treatment received during the prior double-blind period.

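### For patients who reached open label, AEs missing both start and end dates leave the double-blind TEAE tables, so the rule is not worst-case for the randomised comparison

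*SAP*

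**What the plan says.** **Undated AEs.** SAP 6.2.5 sets the default: "AEs with missing start and end dates will be considered as treatment emergent for the open-label period". It describes this as a worst-case choice. The next sentence gives two exceptions, "If the patient has not yet reached the open-label period, or if the AE has a stop date overlapping with the double-blind study period", and in either case "the AE will be counted as treatment-emergent for the double-blind period". The section has no rule for partial AE dates.

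**Tables affected.** SAP 4.11 keeps the periods apart: "Tables using the Double-Blind Safety Population will include only data collected during the" double-blind period. The same section builds the Fosmetpantotenate Safety Population tables from data after first exposure to drug, which means "open-label data only for patients first administered fosmetpantotenate at baseline of the open-label period". Protocol 6.5.2.2 gives active drug to everyone in the extension: "All patients (regardless of randomization assignment for the double-blind period) will initiate treatment with fosmetpantotenate in the open-label period".

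**Undated medications.** Where SAP 6.2.4 cannot place a medication from its dates, "the medication will be counted as concomitant for the double-blind period and open-label period", provided the patient has reached the extension.

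**The concern.** The double-blind TEAE tables are the only place where drug and placebo are compared under randomisation. A rule that moves an event of unknown onset out of those tables can only lower the counts there. Worst-case is therefore the wrong description for that comparison, even though it fits the tables of drug-exposed experience.

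There is a second consequence. Everyone in the extension takes fosmetpantotenate, so an undated event in a former placebo patient is tabulated as emergent on drug, although it may have begun on placebo or before any dose.

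The wording also does not work as written. The rule is stated for AEs missing both dates, but its second exception needs a stop date. A programmer has to guess whether the rule was meant to include AEs that lack only the start date.

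**Working it through.** The documents state no figure on this point, so there is none to reproduce. The check is a reading of the rule, followed by an illustration of size.

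**Step 1. Where an AE goes under SAP 6.2.5**

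| Patient and AE | Period counted |
|---|---|
| Not yet in open label, both dates missing | Double-blind (first exception) |
| In open label, stop date overlaps double-blind, start date missing | Double-blind (second exception), if the rule is read as covering a missing start date alone |
| In open label, both dates missing | Open label, and by implication not double-blind |
| Start date known | Rule does not apply |

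The third row is the point at issue.

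**Step 2. How many patients fall under the default.** SAP 4.3 times the primary analysis after every patient has finished or left the double-blind period. SAP 4.2 plans 82 randomised and at least 74 completers. If all completers enter the extension (an assumption), the share is c = 74/82 = 0.902. The default is therefore the usual case for an undated AE.

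**Step 3. Largest effect of one patient.** Randomisation is 1:1, so 82/2 = 41 per arm if all are dosed. One patient moves a preferred-term incidence by 1/41 = 2.4 percentage points. This is a ceiling: SAP 4.11.1 counts a patient once per preferred term, so a patient with another dated event under the same term changes nothing.

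**Step 4. Illustration over a range.** Let f be the share of patients with a double-blind AE whose only such AE is fully undated. Assume f is equal in both arms and independent of reaching open label, and that the events truly began in the double-blind period. The share lost from the double-blind tables is f × c. Assume also true incidences of 20% on placebo and 40% on drug, a difference of 20 points. The tabulated difference is 20 × (1 − f × c), and the expected number of placebo patients whose event moves to drug-exposed time is 41 × 0.20 × f × c.

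| f (assumed) | Share lost | Risk difference (points) | Placebo patients moved |
|---|---|---|---|
| 1% | 0.9% | 19.8 | 0.07 |
| 5% | 4.5% | 19.1 | 0.37 |
| 10% | 9.0% | 18.2 | 0.74 |
| 20% | 18.0% | 16.4 | 1.48 |

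The risk ratio stays at 40/20 = 2.0 throughout, because both arms lose the same share. If such AEs were counted in both periods, the share lost would be 0.

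**Step 5. Comparison with the medication rule.** SAP 6.2.4 resolves the same uncertainty by counting both periods. SAP 6.2.5 picks one, and the one it picks is outside the controlled comparison.

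**The case against.** The case for leaving the rule alone has real content.

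- **Direction.** Sending the event to open label makes drug-exposed incidence look worse. For the open-label and Fosmetpantotenate Safety Population tables the worst-case label is fair. This stands, but it does not cover the double-blind tables.
- **Unknown onset.** Protocol 10.5.1 collects AEs from consent, so an undated event may be pre-dose, double-blind or open-label. A reader might infer that the plan attributes placebo-arm events to drug. The documents support only a possible misattribution. SAP 6.1.4 also gives separate open-label columns by prior arm, so such events are not hidden.
- **Exceptions.** A reader might infer that every AE with a missing date leaves the double-blind tables. The two exceptions, and the restriction to AEs missing both dates, rule that out.
- **No shown bias towards drug.** Events leave from both arms. With equal missingness the risk difference shrinks and the risk ratio is unchanged. Nothing in the documents says missingness would differ by arm.
- **Rarity.** Protocol 10.1 has AEs reviewed at every visit or contact, and Protocol 13.4.2 disallows blank eCRF fields and has incomplete entries queried. Fully undated AEs should be few.
- **Weak analogy.** Medication use spans time, and SAP 4.8.1 lets chronic medications count in every period, whereas treatment emergence turns on one onset or worsening. The medication rule is a precedent for inclusive counting, and the difference between the two rules is not itself an error.
- **Limits of the remedy.** Counting in both periods still tabulates a former placebo patient's event as on drug. This is correct, and it is why the listing flag is needed.

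Together these points limit the size and the wording of the concern. None of them puts the undated events back into the randomised comparison.

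**Conclusion.** The point holds in a narrow form. For a patient who reached open label, an AE with neither date is counted in open label and lost to the double-blind TEAE tables, although it may have begun there. The rule is conservative for drug-exposed incidence and not for the randomised comparison. A former placebo patient's event may be shown as emergent on fosmetpantotenate. The stop-date exception cannot operate on an AE that has no dates.

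The expected effect is small: at most 2.4 percentage points per affected patient for a preferred term, assuming 41 dosed per arm. The total depends on the number of undated AEs, which the documents do not give. The 1% to 20% range above is assumed, as is entry of all completers into the extension. The documents do not show that double-blind incidence is in fact understated or that the comparison favours the drug. Either conclusion would need the true onset of the events and their distribution by arm. This is a minor improvement to the plan.

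**What to change.** Revise SAP 6.2.5 so that:

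1. For patients who reached open label, an AE whose onset cannot be placed is treatment-emergent in both the double-blind and the open-label tables, unless a known or partial date rules a period out.
2. The rule expressly covers a missing start date, with or without a stop date, so that the stop-date condition has something to act on.
3. These AEs carry a flag in the by-patient AE listing, so that former placebo patients' events can be read with that caveat. The listing in SAP 4.11.1 already shows onset and resolution dates and study period, so this adds one marker.

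The cost is a few sentences in the SAP and a small programming change, with no new data. The drawback is that some pre-dose or open-label events may enter the double-blind tables, in both arms. The change does not remove the possible on-drug count for former placebo patients; it only makes it visible.
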